4.2 Treatment Plan

The treatment to be used in this trial is outlined in Table 1 below.

Drug	Dose/Potency	Dose Frequency	Route of Administration	Regimen/ Treatment Period	Use
pembrolizumab	200 mg	Every 3 weeks	IV infusion	Up to 24 months or until meet drug discontinuation criteria (See 4.5)	Experimental

Drug	Dose/Potency	Dose Frequency	Route of Administration	Regimen/ Treatment Period	Use
The pembrolizumab dosing interval may be increased due to toxicity described in 4.2.2 .					

Based on our experience with very minimal side effects observed in the first 3 evaluable patients (see Table 2) as well as the design of another adjuvant Pembrolizumab study ongoing in triple negative breast cancer, physician follow-up will be reduced to every 2 cycles during the study due to the known side effect profile of Pembrolizumab.

Table 2: Interim safety analysis (3 evaluable patients, as of November 2017)

AE	Grade	Total # of patients
Fatigue	Grade 1	2
Nausea	Grade 1	1
Hot flashes	Grade 1	2
Headaches	Grade 1	1
Agitation	Grade 1	1
Skin itching	Grade 1	2
Vomiting	Grade 1	1
Dizziness	Grade 1	1
Eye disorders - eyelash thinning	Grade 1	1
Arthalgia	Grade 1	1
Rash	Grade 1	1

Based on emerging safety and efficacy data, as described in section 3.1.4, study treatment may be given concurrently with radiation based on physician and/or patient preference, but is not required. For patients consented prior to radiation who meet other eligibility criteria to allow concurrent radiation, pembrolizumab treatment will begin 7 days (± 3 days) after initiating radiation. During radiation, adverse events will be collected weekly, and patients will continue twice-weekly/weekly follow up visits with radiation oncologists as per standard procedure at MD Anderson for IBC patients receiving radiation. Special attention will be placed to minimize off-target dose to the lung, owing to the risk for pneumonitis in patients receiving immune checkpoint therapy.

4.2.1 Dose Selection

4.2.1.1 pembrolizumab: Each cycle is defined as 3-week interval. pembrolizumab 200 mg will be administered on day 1 of each cycle as approximately 30 minute IV infusion (treatment cycle intervals may be increased due to toxicity as described in Section [4.2.2](#)). Pembrolizumab may be administered up to 3 days before or after the scheduled Day 1 of each cycle due to administrative reasons.

The Procedures Manual contains specific instructions for pembrolizumab dose calculation, reconstitution, preparation of the infusion fluid, and administration.

4.2.1.2 Hormonal Therapy: The hormone receptor blockade agent would be on physicians' discretion including tamoxifen, exemestane, anastrozole, letrozole, LHRH agonist and combination with any of above.

4.2.2 Dose Modification

Adverse events (both non-serious and serious) associated with pembrolizumab exposure may represent an immunologic etiology. These adverse events may occur shortly after the first dose or several months after the last dose of treatment. Pembrolizumab must be withheld for drug-related toxicities and severe or life-threatening AEs as per Table 3 below. See [Section 4.4](#) for supportive care guidelines, including use of corticosteroids.

Table 3 Dose Modification Guidelines for pembrolizumab Related Adverse Events:

Toxicity	Hold Treatment For Grade	Timing for Restarting Treatment	Treatment Discontinuation
Diarrhea/Colitis	2-3	Toxicity resolves to Grade 0-1	Toxicity does not resolve within 12 weeks of last dose or inability to reduce corticosteroid to 10 mg or less of prednisone or equivalent per day within 12 weeks
	4	Permanently discontinue	Permanently discontinue
AST, ALT, or Increased Bilirubin	2	Toxicity resolves to Grade 0-1	Toxicity does not resolve within 12 weeks of last dose
	3-4	Permanently discontinue	Permanently discontinue
Type 1 diabetes mellitus (if new onset) or Hyperglycemia	T1DM or 3-4	Hold pembrolizumab for new onset Type 1 diabetes mellitus or Grade 3-4 hyperglycemia associated with evidence of beta cell failure	Resume pembrolizumab when patients are clinically and metabolically stable
Hypophysitis	2-4	Toxicity resolves to Grade 0-1. Therapy with pembrolizumab can be continued while endocrine replacement therapy is instituted	Toxicity does not resolve within 12 weeks of last dose or inability to reduce corticosteroid to 10 mg or less of prednisone or equivalent per day within 12 weeks
Hyperthyroidism	3	Toxicity resolves to Grade 0-1	Toxicity does not resolve within 12 weeks of last dose or inability to reduce corticosteroid to 10 mg or less of prednisone or equivalent per day within 12 weeks
	4	Permanently discontinue	Permanently discontinue
Hypothyroidism		Therapy with pembrolizumab can be continued while thyroid replacement therapy is instituted	Therapy with pembrolizumab can be continued while thyroid replacement therapy is instituted
Infusion Reaction	2 ^a	Toxicity resolves to Grade 0-1	Permanently discontinue if toxicity develops despite adequate premedication
	3-4	Permanently discontinue	Permanently discontinue
Pneumonitis	2	Toxicity resolves to Grade 0-1	Toxicity does not resolve within 12 weeks of last dose or inability to reduce corticosteroid to 10 mg or less of prednisone or equivalent per day within 12 weeks
	3-4	Permanently discontinue	Permanently discontinue
Renal Failure or Nephritis	2	Toxicity resolves to Grade 0-1	Toxicity does not resolve within 12 weeks of last dose or inability to reduce corticosteroid to 10 mg or less of prednisone or equivalent per day within 12 weeks

Toxicity	Hold Treatment For Grade	Timing for Restarting Treatment	Treatment Discontinuation
	3-4	Permanently discontinue	Permanently discontinue
All Other Drug-Related Toxicity ^b	3 or Severe	Toxicity resolves to Grade 0-1	Toxicity does not resolve within 12 weeks of last dose or inability to reduce corticosteroid to 10 mg or less of prednisone or equivalent per day within 12 weeks
	4	Permanently discontinue	Permanently discontinue

Note: Permanently discontinue for any severe or Grade 3 drug-related AE that recurs or any life-threatening event.

^a If symptoms resolve within one hour of stopping drug infusion, the infusion may be restarted at 50% of the original infusion rate (e.g., from 100 mL/hr to 50 mL/hr). Otherwise dosing will be held until symptoms resolve and the subject should be premedicated for the next scheduled dose; Refer to section 4.4 Table 4 – Infusion Treatment Guidelines for further management details.

^b Patients with intolerable or persistent Grade 2 drug-related AE may hold study medication at physician discretion. Permanently discontinue study drug for persistent Grade 2 adverse reactions for which treatment with study drug has been held, that do not recover to Grade 0-1 within 12 weeks of the last dose.

Dosing interruptions are permitted in the case of medical / surgical events or logistical reasons not related to study therapy (e.g., elective surgery, unrelated medical events, patient vacation, and/or holidays). Subjects should be placed back on study therapy within 3 weeks of the scheduled interruption, unless otherwise discussed with the Sponsor. The reason for interruption should be documented in the patient's study record.

In case toxicity does not resolve to Grade 0-1 or baseline within 12 weeks after last infusion, trial treatment will be discontinued. Subjects with a laboratory adverse event still at Grade 2 after 12 weeks may continue treatment in the trial only if asymptomatic and controlled.

Subjects who experience a recurrence of the same severe or life-threatening event at the same grade or greater with re-challenge of pembrolizumab will be discontinued from trial treatment.

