7.5 Evaluating Adverse Events

An investigator who is a qualified physician will evaluate all adverse events according to the NCI Common Terminology for Adverse Events (CTCAE), version 4.0. Any adverse event which changes CTCAE grade over the course of a given episode will have each change of grade recorded on the adverse event case report forms/worksheets.

All adverse events regardless of CTCAE grade must also be evaluated for seriousness.

An investigator who is a qualified physician, will evaluate all adverse events as to:

V4.0 CTCAE Grading	Grade 1	Mild; asymptomatic or mild symptoms; clinical or diagnostic observations only; intervention not indicated.
	Grade 2	Moderate; minimal, local or noninvasive intervention indicated; limiting age-appropriate instrumental ADL.
	Grade 3	Severe or medically significant but not immediately life-threatening; hospitalization or prolongation of hospitalization indicated; disabling; limiting self-care ADL.
	Grade 4	Life threatening consequences; urgent intervention indicated.
	Grade 5	Death related to AE

Seriousness	A serious adverse event is any adverse event occurring at any dose or during any use of Merck product that:
	† Results in death ; or
	† Is life threatening ; or places the subject, in the view of the investigator, at immediate risk of death from the event as it occurred (Note: This does not include an adverse event that, had it occurred in a more severe form, might have caused death.); or
	† Results in a persistent or significant disability/incapacity (substantial disruption of one's ability to conduct normal life functions); or
	† Results in or prolongs an existing inpatient hospitalization (hospitalization is defined as an inpatient admission, regardless of length of stay, even if the hospitalization is a precautionary measure for continued observation. (Note: Hospitalization for an elective procedure to treat a pre-existing condition that has not worsened is not a serious adverse event. A pre-existing condition is a clinical condition that is diagnosed prior to the use of a Merck product and is documented in the patient's medical history.); or
	† Is a congenital anomaly/birth defect (in offspring of subject taking the product regardless of time to diagnosis); or
	Is a new cancer (that is not a condition of the study) (although not serious per ICH definition, is reportable to the Sponsor and Merck); or

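### Table 3 lets pembrolizumab restart at Grade 0-1, just as the steroid taper begins, with no steroid ceiling at restart; the Grade 2 hepatic row also lacks the 10 mg stop limit

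*Combined protocol and SAP*

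**What the plan says.** **Restart.** In Table 3 (Section 4.2.2) the restart column for colitis, hepatic events, hypophysitis, hyperthyroidism, pneumonitis, renal events and the "All Other Drug-Related Toxicity" row reads "Toxicity resolves to Grade 0-1". No steroid dose is attached. The hypophysitis cell adds "Therapy with pembrolizumab can be continued while endocrine replacement therapy is instituted".

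**Stopping.** In those rows, except the hepatic one, the discontinuation column adds "inability to reduce corticosteroid to 10 mg or less of prednisone or equivalent per day within 12 weeks". The Grade 2 part of the row headed "AST, ALT, or Increased Bilirubin" has only the 12-week limit on the toxicity itself.

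**Laboratory exception.** Below the table: "Subjects with a laboratory adverse event still at Grade 2 after 12 weeks may continue treatment in the trial only if asymptomatic and controlled".

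**Steroid treatment.** Section 4.4 gives corticosteroids for Grade 2 pneumonitis, hepatic and renal events, for hypophysitis, for Grade 3-4 hyperthyroidism, and for colitis that persists (Grade 2 beyond 3 days, Grade 3-4 beyond 1 week). In each case the taper begins at Grade 1 or below and lasts at least four weeks. The section also warns that symptoms can return as the dose comes down.

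**Other steroid rules.** Exclusion 15 bars patients who need daily corticosteroids. Section 4.3 carries the exclusion-criteria prohibitions into the trial. Section 4.3.2 bans glucocorticoids but exempts those given for suspected immune-related symptoms. Section 4.5.3 limits only the length of a treatment interruption.

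**The concern.** The restart criterion and the start of the taper share one trigger. At the first moment restart is allowed, the patient may be on the full steroid dose, and a grade of 0-1 may reflect suppression rather than recovery. Giving another infusion then re-exposes the patient to the likely cause just as the treatment for it is withdrawn.

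The protocol has a tolerance in mind, 10 mg/day, but uses it only to decide who must stop, not who may resume. For Grade 2 hepatic events it uses it for neither. What is at stake is avoidable immune toxicity in adjuvant patients without known distant metastasis.

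**Working it through.** There is no plan figure to reproduce here. The check compares the sections row by row and then does the timing arithmetic.

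**1. Where restart and taper coincide.**

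| Event that may restart (Table 3) | Taper from Grade 0-1 in 4.4 | 10 mg stop limb |
|---|---|---|
| Colitis, Grade 2-3 | Yes, if steroids were given | Yes |
| Hepatic, Grade 2 | Yes | **No** |
| Hypophysitis | Yes | Yes |
| Hyperthyroidism, Grade 3 | Yes | Yes |
| Pneumonitis, Grade 2 | Yes | Yes |
| Renal, Grade 2 | Yes | Yes |
| All other, Grade 3 | None given | Yes |

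Hypophysitis is listed as Grade 2-4. The note to Table 3, "Permanently discontinue for any severe or Grade 3 drug-related AE that recurs or any life-threatening event", read with the Grade 4 description in Section 7.5, "Life threatening consequences; urgent intervention indicated", removes Grade 4. Grade 3-4 pneumonitis, hepatic and renal events stop permanently, so in those rows the issue is an improved Grade 2 event.

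**2. Whether another section supplies a ceiling.** Exclusion 15 read through Section 4.3 would ban daily steroids on study. Section 4.3.2 specifically exempts immune-related use, and Section 4.4 directs it. The 10 mg limb itself presupposes that a patient can continue on a low daily dose. None of these sections sets a dose for restart.

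**3. The laboratory exception.** It relaxes only the need to reach Grade 0-1. Where a row has the 10 mg limb, that limb still stops treatment. The hepatic row has none, so a liver test still at Grade 2 after 12 weeks may continue as controlled, a term the protocol does not define, whatever the steroid dose.

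**4. Timing.** Inputs: 21-day cycle and 3-day window (Section 4.2.1.1); minimum taper 28 days (Section 4.4); 34 cycles (Section 5.0, footnote e).

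- Latest next scheduled infusion after Grade 0-1: 21 + 3 = 24 days. Taper days left: 28 − 24 = 4, or 28 − 21 = 7 without the window.
- Scheduled Day 1s inside a 28-day wait: 1 or 2. Maximum share of treatment: 2/34 = 5.9%.
- Latest Grade 0-1 that leaves room for a full minimum taper by week 12: 84 − 28 = 56 days, or week 8.

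**5. Illustration (assumption).** The documents give no starting dose. Assume a linear taper from D mg to zero over 28 days. The dose on day t is D × (1 − t/28), and 10 mg is reached on day 28 × (1 − 10/D). If the time to the next Day 1 is uniform over 0 to 21 days, the mean number of infusions delayed under a 10 mg rule is that day divided by 21.

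| D (mg) | Day 10 mg reached | Dose day 0 | Dose day 21 | Dose day 24 | Mean infusions delayed |
|---|---|---|---|---|---|
| 20 | 14.0 | 20 | 5 | 2.9 | 0.67 |
| 40 | 21.0 | 40 | 10 | 5.7 | 1.00 |
| 60 | 23.3 | 60 | 15 | 8.6 | 1.11 |
| 80 | 24.5 | 80 | 20 | 11.4 | 1.17 |
| 100 | 25.2 | 100 | 25 | 14.3 | 1.20 |

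An infusion at the first permitted moment is given at the full starting dose. The latest one, on day 24, is at or below 10 mg whenever D × 4/28 ≤ 10, that is, for starts up to 70 mg.

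**The case against.** **The 10 mg limit is already implied.** Six rows stop treatment if steroids cannot be brought down, which makes most sense if drug stays held meanwhile. That is a fair reading of intent, and it makes the fix largely a clarification for those rows. But it is not written as a restart condition. A patient restarted on a high dose can still satisfy the stop limb weeks later, and the hepatic row has no limb from which to imply anything.

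**Safeguards exist.** Restart is optional and intervals may be lengthened for toxicity. Adverse events are reviewed before each dose, and Section 4.4 advises closer liver monitoring. Section 4.2.2 discontinues a patient whose severe event recurs on re-challenge. The Section 4.4 measures are suggestions, and this is one center. All of this stands and limits the size of the point. These measures mostly detect a flare after re-exposure; none gives a dose at which to resume.

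**Stronger readings do not hold.** A reader might infer that the laboratory exception is open-ended in every row; it is so only in the hepatic row. A reader might infer a restart/taper overlap for the all-other row; Section 4.4 gives no taper there. A reader might take the 4 remaining taper days as proof of dosing above 10 mg; step 5 shows that they are not.

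**Conclusion.** The gap is real on the text. Table 3 permits, without requiring, re-treatment at the point where a taper of at least four weeks begins, for the six event types with a taper in the table above. It sets no steroid dose for doing so. The Grade 2 hepatic row also lacks the 12-week steroid limit that the comparable rows carry, which leaves the laboratory exception without a steroid limit for liver tests.

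The next scheduled infusion falls within 24 days, before a 28-day taper ends. How often a site would restart early, and on what dose, cannot be derived from the documents; the dose and mean-delay figures rest on the assumed linear taper and uniform timing. This is a patient-safety clarification and a cheap improvement. Nothing in the documents supports reading it as a threat to the primary endpoint, sample size or error rates.

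**What to change.** In Section 4.2.2:

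- After any event treated with systemic steroids, require both Grade 0-1 and no more than 10 mg/day prednisone equivalent before the next infusion. Exempt physiologic hormone replacement in hypophysitis, so that its continuation sentence still works.
- Add the 10 mg/12-week limb to the Grade 2 hepatic row. The laboratory exception can then stay: it relaxes the grade, and the limb governs the steroid dose.
- State that holds under this rule are not major violations under Section 4.6.1.3, which lists treatment delays of 7 days or more.

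**Cost.** Two sentences and one table entry; no added visits or tests. On a minimum taper at most 2 infusions per event are delayed, and longer tapers delay more. If the 12 weeks run from the last dose, some hepatic patients who resolve between weeks 8 and 12 may be discontinued because they cannot finish a taper in time. The steroid dose must be checked in the medical record, because Section 10.1 keeps concomitant medication out of the study database.

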4.3 Concomitant Medications/Vaccinations (allowed & prohibited)

Medications or vaccinations specifically prohibited in the exclusion criteria are not allowed during the ongoing trial. If there is a clinical indication for one of these or other medications or vaccinations specifically prohibited during the trial, discontinuation from trial therapy or vaccination may be required. The final decision on any supportive therapy or vaccination rests with the investigator and/or the subject's primary physician.

4.3.1 Acceptable Concomitant Medications

All treatments that the investigator considers necessary for a subject's welfare may be administered at the discretion of the investigator in keeping with the community standards of medical care. Concomitant medication will be recorded as standard of care in clinic database.

4.3.2 Prohibited Concomitant Medications

Subjects are prohibited from receiving the following therapies during the study.

- Live vaccines within 30 days prior to the first dose of trial treatment and while participating in the trial. Examples of live vaccines include, but are not limited to, the following: measles, mumps, rubella, chicken pox, yellow fever, rabies, BCG, and typhoid (oral)

vaccine. Seasonal influenza vaccines for injection are generally killed virus vaccines and are allowed; however intranasal influenza vaccines (e.g. Flu-Mist®) are live attenuated vaccines, and are not allowed.

- Glucocorticoids for any purpose other than to modulate symptoms of suspected immunologic etiology.

Subjects who, in the assessment by the investigator, require the use of any of the aforementioned treatments for clinical management should be removed from the trial. Subjects may receive other medications that the investigator deems to be medically necessary.

There are no prohibited therapies during the Post-Treatment Follow-up Phase.

4.4 Rescue Medications & Supportive Care

Subjects should receive appropriate supportive care measures as deemed necessary by the treating investigator. Suggested supportive care measures for the management of adverse events with potential immunologic etiology are outlined below. Where appropriate, these guidelines include the use of oral or intravenous treatment with corticosteroids as well as additional anti-inflammatory agents if symptoms do not improve with administration of corticosteroids. Note that several courses of steroid tapering may be necessary as symptoms may worsen when the steroid dose is decreased. For each disorder, attempts should be made to rule out other causes such as metastatic disease or bacterial or viral infection, which might require additional supportive care. The treatment guidelines are intended to be applied when the investigator determines the events to be related to pembrolizumab.

Subjects should receive appropriate supportive care measures as deemed necessary by the treating investigator. Suggested supportive care measures for the management of adverse events with potential immunologic etiology are outlined below. Where appropriate, these guidelines include the use of oral or intravenous treatment with corticosteroids as well as additional anti-inflammatory agents if symptoms do not improve with administration of corticosteroids. Note that several courses of steroid tapering may be necessary as symptoms may worsen when the steroid dose is decreased. For each disorder, attempts should be made to rule out other causes such as metastatic disease or bacterial or viral infection, which might require additional supportive care. The treatment guidelines are intended to be applied when the investigator determines the events to be related to pembrolizumab.

Note: if after the evaluation the event is determined not to be related, the investigator does not need to follow the treatment guidance (as outlined below). Refer to Table 3 for dose modification.

It may be necessary to perform conditional procedures such as bronchoscopy, endoscopy, or skin photography as part of evaluation of the event.

- **Pneumonitis:**
 - For **Grade 2 events**, treat with systemic corticosteroids. When symptoms improve to Grade 1 or less, steroid taper should be started and continued over no less than 4 weeks.

- For **Grade 3-4 events**, immediately treat with intravenous steroids. Administer additional anti-inflammatory measures, as needed.
- Add prophylactic antibiotics for opportunistic infections in the case of prolonged steroid administration.
- **Diarrhea/Colitis:**
Subjects should be carefully monitored for signs and symptoms of enterocolitis (such as diarrhea, abdominal pain, blood or mucus in stool, with or without fever) and of bowel perforation (such as peritoneal signs and ileus).
 - All subjects who experience diarrhea/colitis should be advised to drink liberal quantities of clear fluids. If sufficient oral fluid intake is not feasible, fluid and electrolytes should be substituted via IV infusion. For Grade 2 or higher diarrhea, consider GI consultation and endoscopy to confirm or rule out colitis.
 - For **Grade 2 diarrhea/colitis** that persists greater than 3 days, administer oral corticosteroids.
 - For **Grade 3 or 4 diarrhea/colitis** that persists > 1 week, treat with intravenous steroids followed by high dose oral steroids.
 - When symptoms improve to Grade 1 or less, steroid taper should be started and continued over no less than 4 weeks.
- **Type 1 diabetes mellitus (if new onset, including diabetic ketoacidosis [DKA]) or ≥ Grade 3 Hyperglycemia, if associated with ketosis (ketonuria) or metabolic acidosis (DKA)**
 - For **T1DM** or **Grade 3-4 Hyperglycemia**
 - Insulin replacement therapy is recommended for Type I diabetes mellitus and for Grade 3-4 hyperglycemia associated with metabolic acidosis or ketonuria.
 - Evaluate patients with serum glucose and a metabolic panel, urine ketones, glycosylated hemoglobin, and C-peptide.
- **Hypophysitis:**
 - For **Grade 2** events, treat with corticosteroids. When symptoms improve to Grade 1 or less, steroid taper should be started and continued over no less than 4 weeks. Replacement of appropriate hormones may be required as the steroid dose is tapered.
 - For **Grade 3-4** events, treat with an initial dose of IV corticosteroids followed by oral corticosteroids. When symptoms improve to Grade 1 or less, steroid taper should be started and continued over no less than 4 weeks. Replacement of appropriate hormones may be required as the steroid dose is tapered.
- **Hyperthyroidism or Hypothyroidism:**
Thyroid disorders can occur at any time during treatment. Monitor patients for changes in thyroid function (at the start of treatment, periodically during treatment, and as indicated based on clinical evaluation) and for clinical signs and symptoms of thyroid disorders.
 - **Grade 2** hyperthyroidism events (and **Grade 3-4** hypothyroidism):
 - In hyperthyroidism, non-selective beta-blockers (e.g. propranolol) are suggested as initial therapy.

- In hypothyroidism, thyroid hormone replacement therapy, with levothyroxine or liothyroinine, is indicated per standard of care.
- **Grade 3-4** hyperthyroidism
 - Treat with an initial dose of IV corticosteroid followed by oral corticosteroids. When symptoms improve to Grade 1 or less, steroid taper should be started and continued over no less than 4 weeks. Replacement of appropriate hormones may be required as the steroid dose is tapered.
- **Hepatic:**
 - For **Grade 2** events, monitor liver function tests more frequently until returned to baseline values (consider weekly).
 - Treat with IV or oral corticosteroids
 - For **Grade 3-4** events, treat with intravenous corticosteroids for 24 to 48 hours.
 - When symptoms improve to Grade 1 or less, a steroid taper should be started and continued over no less than 4 weeks.
- **Renal Failure or Nephritis:**
 - For **Grade 2** events, treat with corticosteroids.
 - For **Grade 3-4** events, treat with systemic corticosteroids.
 - When symptoms improve to Grade 1 or less, steroid taper should be started and continued over no less than 4 weeks.
- **Management of Infusion Reactions:** Signs and symptoms usually develop during or shortly after drug infusion and generally resolve completely within 24 hours of completion of infusion

Table 4 below shows treatment guidelines for subjects who experience an infusion reaction associated with administration of pembrolizumab.

Table 4 Infusion Reaction Treatment Guidelines

NCI CTCAE Grade	Treatment	Premedication at subsequent dosing
Grade 1 Mild reaction; infusion interruption not indicated; intervention not indicated	Increase monitoring of vital signs as medically indicated until the subject is deemed medically stable in the opinion of the investigator.	None
Grade 2 Requires infusion interruption but responds promptly to symptomatic treatment (e.g., antihistamines, NSAIDS, narcotics, IV fluids); prophylactic medications indicated for <=24 hrs	Stop Infusion and monitor symptoms. Additional appropriate medical therapy may include but is not limited to: IV fluids Antihistamines NSAIDS Acetaminophen Narcotics Increase monitoring of vital signs as medically indicated until the subject is deemed medically stable in the opinion of the investigator. If symptoms resolve within one hour of stopping drug infusion, the infusion may be restarted at 50% of the	Subject may be premedicated 1.5h (\pm 30 minutes) prior to infusion of pembrolizumab with: Diphenhydramine 50 mg po (or equivalent dose of antihistamine). Acetaminophen 500-1000 mg po (or equivalent dose of antipyretic).

NCI CTCAE Grade	Treatment	Premedication at subsequent dosing
	
original infusion rate (e.g. from 100 mL/hr to 50 mL/hr). Otherwise dosing will be held until symptoms resolve and the subject should be premedicated for the next scheduled dose.
 
Subjects who develop Grade 2 toxicity despite adequate premedication should be permanently discontinued from further trial treatment administration.
	
Grades 3 or 4 Grade 3: Prolonged (i.e., not rapidly responsive to symptomatic medication and/or brief interruption of infusion); recurrence of symptoms following initial improvement; hospitalization indicated for other clinical sequelae (e.g., renal impairment, pulmonary infiltrates) Grade 4: Life-threatening; pressor or ventilatory support indicated	
Stop Infusion.
 
Additional appropriate medical therapy may include but is not limited to:
 
IV fluidsAntihistaminesNSAIDSAcetaminophenNarcoticsOxygenPressorsCorticosteroidsEpinephrine 
Increase monitoring of vital signs as medically indicated until the subject is deemed medically stable in the opinion of the investigator. Hospitalization may be indicated. Subject is permanently discontinued from further trial treatment administration.
	No subsequent dosing

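### Section 4.4 suggests steroids later for Grade 3-4 diarrhea/colitis (after more than 1 week) than for Grade 2 (after more than 3 days)

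*Combined protocol and SAP*

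**What the plan says.** Section 4.4 (Rescue Medications & Supportive Care) treats diarrhea/colitis in two adjacent lines, split by grade.

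- Grade 2: "that persists greater than 3 days, administer oral corticosteroids".
- Grade 3 or 4: "that persists > 1 week, treat with intravenous steroids followed by high dose oral steroids".

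The same block advises fluids, monitoring for enterocolitis and bowel perforation, and a work-up: "For Grade 2 or higher diarrhea, consider GI consultation and endoscopy to confirm or rule out colitis".

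The introduction to Section 4.4 calls these measures suggestions, asks that other causes such as infection be ruled out, and says the guidance is meant for events the investigator judges related to pembrolizumab. Section 4.2.2 refers the reader to Section 4.4 for the use of corticosteroids. Table 3 in Section 4.2.2 holds pembrolizumab for Grade 2-3 diarrhea/colitis and stops it permanently at Grade 4. It mentions steroids for this event only as a taper criterion for discontinuation, not as a rule for when to start them.

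**The concern.** A steroid trigger should come no later for a more severe event than for a milder one. Here it comes later. The Grade 2 line is limited to Grade 2 and does not cover a patient who presents at Grade 3 or 4, or who worsens to that grade before the 3-day condition is met. For that patient Section 4.4 offers no steroid line until the event has lasted more than a week.

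The protocol's own grading table (Section 7.5) describes Grade 3 as severe, with hospitalization indicated, and Grade 4 as life threatening and needing urgent intervention. A one-week persistence condition does not fit those definitions. At stake is patient safety in the section the protocol designates for steroid guidance: a clinician who takes the line as the trigger would start steroids later in the sicker patient.

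**Working it through.** No sample size, power or error rate is involved. The check compares the two triggers and then sets them beside the rest of Section 4.4.

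**Step 1: size of the inversion.** Inputs are the two durations in the diarrhea/colitis block: more than 3 days (Grade 2) and more than 1 week, i.e. 7 days (Grade 3-4).

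- Difference: 7 - 3 = 4 days later at the higher grade.
- Ratio: 7 / 3 = 2.33.

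**Step 2: comparison with the other organ toxicities that use steroids at Grade 3-4 in Section 4.4.**

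| Toxicity | Grade 2 | Grade 3-4 | Wait at Grade 3-4? |
|---|---|---|---|
| Pneumonitis | Systemic steroids, no wait | "immediately treat with intravenous steroids. Administer additional anti-inflammatory measures, as needed" | No |
| Diarrhea/colitis | Oral steroids after more than 3 days | IV, then high-dose oral, after more than 1 week | **Yes** |
| Hypophysitis | Steroids, no wait | "treat with an initial dose of IV corticosteroids followed by oral corticosteroids" | No |
| Hyperthyroidism | No steroid line: "In hyperthyroidism, non-selective beta-blockers (e.g. propranolol) are suggested as initial therapy" | "Treat with an initial dose of IV corticosteroid followed by oral corticosteroids" | No |
| Hepatic | IV or oral steroids, no wait | "treat with intravenous corticosteroids for 24 to 48 hours" | No |
| Renal failure/nephritis | Steroids, no wait | Systemic steroids | No |

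Infusion reactions are not counted because they are not an organ toxicity. Table 4 lists corticosteroids among the options at Grade 3-4 and sets no wait.

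- Toxicities using steroids at Grade 3-4: 6. With a waiting period at that grade: 1.
- Toxicities with a steroid line at both Grade 2 and Grade 3-4: 6 - 1 (hyperthyroidism) = 5. With the later trigger at the higher grade: 1. With no wait at either grade: 4 (pneumonitis, hypophysitis, hepatic, renal).

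**Step 3: does anything else in the block run backwards?** No. Treatment intensity rises with grade (oral, then IV followed by high-dose oral), and so does Table 3 (hold, then permanent discontinuation). Only the steroid timing is reversed.

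**Step 4: what the lines imply when a patient worsens.** Take, for illustration, a patient who is Grade 2 for 2 days and then becomes Grade 3. Had she stayed at Grade 2, the oral steroid line would apply after day 3. Once she is Grade 3, the line applies after day 7 if persistence is counted from first onset, or after day 2 + 7 = 9 if it is counted from reaching Grade 3. The text does not say which. On either count, getting worse moves her to a later trigger.

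**Step 5: is there an earlier Grade 3-4 start elsewhere?** None was found. Table 3 governs pembrolizumab dosing. Sections 4.3.1, 4.3.2 and 7.1 permit treatment at the investigator's discretion or when clinically indicated, but none gives a steroid start time for colitis.

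**The case against.** The strongest reply is that the line suggests when to treat and does not instruct anyone to withhold. Section 4.4 leaves supportive care to the treating investigator, Section 4.3.1 allows whatever treatment is considered necessary, the glucocorticoid prohibition in Section 4.3.2 exempts symptoms of suspected immunologic cause, and Section 7.1 allows care as clinically indicated. Table 3 holds or stops the drug with no wait. Exclusion criterion 13 keeps out patients with gastrointestinal disease or prior colitis, and the grading table makes a passive week at Grade 3-4 unlikely in practice. All of this stands, and it limits the consequence. It does not correct the sentence.

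A second reply is that the week leaves time to exclude infection or confirm colitis by endoscopy. That could justify some wait, but not a longer one at the higher grade: the advice to rule out other causes applies to every disorder, and the endoscopy advice applies equally from Grade 2 upward.

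A third is that the Grade 3-4 line is meant as escalation after the 3-day oral step. A patient who worsens after more than 3 days at Grade 2 would indeed already be on oral steroids, so the uncovered group is those who present at Grade 3-4 or reach it sooner. But the text does not describe an escalation, and that group remains uncovered.

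Finally, the documents do not state what the right Grade 3-4 trigger is, and the 2.3-fold ratio compares start times of different steroid regimens. Both are fair. The ratio measures the inversion, not harm. Having no wait is the choice consistent with the other five toxicities.

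**Conclusion.** The concern holds. The suggested steroid start for Grade 3-4 diarrhea/colitis is 4 days later than for Grade 2, and this is the only one of six organ toxicities in Section 4.4 with a wait at Grade 3-4. It is a stated rule that is wrong as written, not a missing detail, and it should be corrected.

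Its reach is limited. The text is advisory, no delay is mandated, the Table 3 dose rules are sound, and the DFS analysis is not affected. The inversion itself is read directly from the text. How often it would delay treatment depends on how clinicians use the guidance and on the colitis rate; the documents give no such rate, so no number of cases or risk of harm is estimated.

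**What to change.** Delete the one-week persistence condition from the Grade 3-4 diarrhea/colitis line, so that it calls for intravenous steroids followed by high-dose oral steroids with no waiting period. The 3-day condition at Grade 2 can stay. The provisions in Section 4.4 on relatedness to pembrolizumab and on ruling out infection still govern the edited line, so it would not direct steroids at diarrhea judged infectious.

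If the sponsor prefers to keep a persistence condition at Grade 3-4, it should be no longer than the 3 days used at Grade 2, and the text should say that it is counted from onset at Grade 2 or higher, so that worsening does not restart the clock.

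The cost is one phrase removed from one line, with no extra visits, tests or patients.
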